**6.3 Describe procedures being performed to monitor subjects for safety or minimize risks.**

Several steps are taken to assure patient safety for surgical procedures. Prior to the procedure, their vitals are taken, including their blood pressure, heart rate, respiratory rate, and oxygen saturation. Depending on the patient, especially those with history of cardiopulmonary disease, monitors are kept cycling every five minutes during the procedure. A thorough history and physical is performed before any procedure to assure appropriate patient selection and to rule out more emergent issues. During the procedure, patients are continuously monitored with active physical examinations by the provider. There is always a certified oral and maxillofacial assistant with the patient in the room, especially during the procedure. For urgent-add on, a registered nurse is normally present as well to monitor the patient. The patient is treated via standard protocol of the oral and maxillofacial clinic at Holmes Hospital, which treats thousands of patients annually through safe, effective, and efficient measures. As explained earlier, emergency crash carts, including rescue airway carts, are present at the facility, as well as dozens of trained personnel promptly available if needed.

**6.5 Where applicable, list and describe the data collection tools such as surveys, data collection forms, etc. All tools described should be uploaded in the RAP Smart Form on the Local Site Documents page unless they are standardized, validated tools.**

Data collection will only be stored and collected on REDCap, which is a server software maintained by Cincinnati Children's Hospital Medical Center (CCHMC) informational technology team. The surgeon assigned to the case will fill out the questionnaire outlining the how effective using the 3D model was during the procedure. The outcome data will then be collected on the same secured software.

**6.6 Describe all data that will be accessed and collected during the study and how that data will be obtained (how it will be accessed).**

Description – Distinguish between data accessed and data collected if applicable.

	6.7 If there is a long-term follow-up plan (once all research related procedures are completed), what data will be collected during this period.
	No Long-Term Follow-Up
7.0 DATA AND SPECIMEN BANKING	7.1 If data or specimens will be banked for future use, describe where the data or specimens will be stored, how the data or specimens will be accessed, and who will have access to the data or specimens. Data collected from this study will be destroyed/deleted after the study's conclusion. No specimens will be collected.
	7.2 If specimens are being stored, list the data to be stored or associated with each specimen. Not Applicable
	7.3 Describe the procedures to release data or specimens, including: (the process to request a data/specimen release, approvals required for release, who can obtain data or specimens, and the data to be provided with the specimens. Not Applicable
8.0 SHARING OF RESULTS WITH SUBJECTS	8.1 Describe whether results (study results or individual subject results, such as results of investigational diagnostic tests, genetic tests, or incidental findings) will be shared with subjects or others (e.g., the subject's primary care physician) and if so, describe the process for sharing. If you do not intend to share any results, please state that here. The results of the study are obtained directly from the questionnaire and involvement. Thus, there is no process to share or release results with patients. Patients will not be sought to discuss the particulars of study results. Study results will be shared via peer-reviewed journals. This section is not pertinent to the study.
9.0 STUDY TIMELINES	9.1 Describe the duration of an individual subject's participation in the study. List the number of study visits or frequency of study visits. The subject's participation is limited to a one-time appointment.
	9.2 Describe the timeline allotted for the enrollment of subjects. Prospective subjects would be triaged during their admissions to UCHMC. If the subject meets the study criteria, the research coordinator would enter the evaluation room after the surgical provider has completed their history and physical, at which point involvement will be established and randomization will be conducted. Thus, based on study design, there is not specific timeline of enrollment since the decision is made same day.
	9.3 Describe the estimated date for the investigators to complete this study (complete primary analysis). Primary analysis is estimated to be complete in January 2024.

**TEMPLATE: RESEARCH PROTOCOL**

NUMBER	ACTIVE DATE	PAGE
HRP-503	02-04-2020	11 of 35

10.0 INCLUSION AND EXCLUSION CRITERIA & VULNERABLE POPULATIONS
	
10.1 Describe how subjects will be screened for eligibility.
 
The screening of potential participants will be performed by the providers of University of Cincinnati Medical Center's Department of Oral and Maxillofacial Surgery clinic located at Holmes Hospital (UCMC OMS HH clinic), or surgical providers from plastic surgery and otolaryngology located in UCMC including resident physicians, attending physicians, research staff, and clinic staff. Surgical team members from the division of plastic and otolaryngology will be consented and recruited to participate in this study by providing their feedback post operatively. The diagnosis and treatment planning will strictly be made by a resident or attending surgeon. However, an elected research coordinator will complete a standardized eligibility form on REDCap based on the study's inclusion/exclusion criteria to finalize participant selection
	
	
10.2 Describe/list the inclusion/exclusion criteria for the study.
 
Inclusion Criteria:
 
Patient ≥ 18 years of age
 
Patients who have received either a cone beam or conventional CT
 
Admitted through UCHMC emergency department
 
All isolated mandible fractures referred to UCH OMS
 
Surgical team members from the division of plastic and otolaryngology
 
Exclusion Criteria:
 
Patient < 18 years of age
 
Patients who have neither cone beam nor conventional CT
 
Patients requiring a repeat procedure
 
Unexpected exposure of hardware
	
	
10.3 Indicate specifically whether you will include each of the following vulnerable populations. Check all that apply. (You may not include members of the below populations as subjects in your research unless you indicate this in your inclusion criteria and are approved by the IRB to include them in your research) The member checklists are for reference only to ensure you provide appropriate safeguards and justification. The checklists do not need to be completed.
	
	
 Adults unable to consent (cognitively impaired individuals) (HRP-417 – MEMBER CHECKLIST Cognitively Impaired)
 
 Individuals who are not yet adults (infants, children, teenagers) (HRP-416 – MEMBER CHECKLIST Children)
 
 Individuals who are not yet adults and are, or may become, wards of the state.
 
 Pregnant women (a woman shall be assumed pregnant if she exhibits and of the presumptive signs of pregnancy, such as a missed menses, until the results
	

**TEMPLATE: RESEARCH PROTOCOL**

NUMBER	ACTIVE DATE	PAGE
HRP-503	02-04-2020	12 of 35

	
of a pregnancy test are negative or until delivery.) (HRP-412 MEMBER CHECKLIST Pregnant Women)
 
 Non-Viable Neonates (HRP-413 – MEMBER CHECKLIST Non-Viable Neonates)
 
 Uncertain Viability Neonates (HRP-414 – MEMBER CHECKLIST Uncertain Viability Neonates)
 
 Prisoners (HRP-415 – MEMBER CHECKLIST Prisoners)
 
10.4 If the research involves individuals listed in 10.3 or other individuals who are vulnerable to coercion or undue influence, please justify based on the applicable checklist and describe additional safeguards included to protect their rights and welfare.
 
N/A
 
10.5 If the research involves or may involve individuals who are students or employees where the research is taking place, please describe additional safeguards included to protect their rights and welfare.
 
Not Applicable

	
11.1 Indicate the total number of subjects to be accrued.
 
We aim to obtain 50 procedures for each arm of the study (100 in total)
 
50: standard surgical procedures aided by use of 3D Printed model
 
50: procedures carried out by standard surgical repair for isolated mandibular fractures (No model)

	
11.2 If applicable, distinguish between the number of subjects who are expected to be enrolled and screened, and the number of subjects needed to complete the research procedures.
 
N/A

	
12.1 Describe when, where, and how potential subjects will be recruited.
 
Subjects of this study are those that require emergent medical attention and are referred to either UCHMS Emergency Department or to UC OMS for treatment. Subjects will be triaged by the clinical providers, and the research coordinator will then complete a standardized informative process. Regardless of involvement, the subject will undergo the same treatment course as any other patient presenting with an isolated mandibular fracture. For the consenting of the surgical team members, they will undergo a research presentation given by the research coordinator in which they have an adequate amount of time to ask any questions or concerns before deciding to be a part of the study.

	
12.2 Describe the source of the subjects.
 
Subjects for the study are any patient are referred to HH OMS for treatment of isolated mandibular fracture. The referral arrives will need emergent medical treatment arriving from the emergency department. No subject will be sought after for the purposes of the study since the population will be emergent cases admit to UCHMC. Surgical team members will be

	
identified by both the PI and research coordinator for recruitment based off of past surgical collaboration on routine procedures at UCMC.
 
12.3 Describe the materials that will be used to recruit subjects. (Attach copies of these documents in the Recruitment section on the local site documents page in RAP. For advertisements, attach the final copy of printed advertisements (avoid making copies until approved in case modifications are required). When advertisements are taped for broadcast, attach the final audio/video tape. You may submit the wording of the advertisement prior to taping to preclude re-taping because of inappropriate wording, provided the IRB reviews the final audio/video tape)
 
N/A

13.0 COMPENSATION FOR SUBJECTS	
13.1 Describe the amount, method, and timing of payments to subjects.
 
N/A

14.0 WITHDRAWAL OF SUBJECTS	
14.1 Describe the anticipated circumstances under which subjects will be withdrawn by the study team from the research without their consent.
 
Given the strict inclusion and exclusion criteria of the study, we anticipate very few circumstances in which patients will need to withdraw by the study team without their consent.
 
14.2 Describe any procedures for orderly termination.
 
Patients will be withdrawn from the study if they unfortunately succumb to their injuries related to any polytrauma that caused the underlying mandibular fracture before any procedures can be completed. Surgeons who no longer wish to provide feedback via the Likert scale questions will also no longer be associated with the study.
 
14.3 Describe procedures that will be followed when subjects withdraw from the research, including partial withdrawal from procedures with continued data collection, withdrawal of previously collected data upon request, etc.
 
Patients and surgeons who are withdrawn from the study for the purposes listed earlier will be excluded from all study results.

15.0 RISKS TO SUBJECTS	
15.1 Describe the reasonably foreseeable risks, discomforts, hazards, or inconveniences to the subjects related to the subjects' participation in the research. It may be useful to include: a description of the probability, magnitude, duration, and reversibility of the risks. Consider the physical, psychological, social, legal, and economic risks.
 
There are no risks related to the 3D printing. The physical model is generated from the CT images that have already been acquired, and the addition of the 3D printed model for those patients randomized to the 3D printing arm will be completely transparent.

**TEMPLATE: RESEARCH PROTOCOL**

NUMBER	ACTIVE DATE	PAGE
HRP-503	02-04-2020	14 of 35

	
The following risks as described are general risks that the patient would assume with the study.
 
Confidentiality of the data
 
Electronic data will contain a de-identified patient ID number, which will be used to link back to the identifier. The key linking identifier to subject number will not be stored with the electronic data. Electronic data will be managed using an excel sheet stored on a secure computer. Analytical datasets will be stored on secure servers that also limit access to the investigator team. Should results of the study be published or reported, individual names or other identifying information will not be used.

	
15.2 If applicable, indicate which procedures may have risks to the subjects that are currently unforeseeable.
 
All procedures and medications used have known risks and are discussed above. Thus, there are no unforeseeable risks to discuss.

	
15.3 If applicable, indicate which procedures may have risks to an embryo or fetus should the subject or the subject's partner be or become pregnant.
 
Not Applicable

	
15.4 If applicable, describe risks to those who are not subjects.
 
Not Applicable

	
15.5 Describe the procedures and actions taken to mitigate the risks to subjects and others.
 
See section 15.1. Each specific risk listed includes a description on mitigation. Since risk and mitigation are synonymous, they have been discussed in the same section.

16.0 POTENTIAL BENEFITS TO SUBJECTS	
16.1 Describe the potential benefits that individual subjects may experience from taking part in the research. It may be useful to include: the probability, magnitude, and duration of the potential benefits. Indicate if there is no direct benefit to subjects. Do not include benefits to society or to others.
 
N/A


17.0 DATA MANAGEMENT AND CONFIDENTIALITY
	
17.1 Describe the data analysis plan, including any statistical procedures or power analyses.
 
We are going to use the Likert questions to develop a numerical scoring system and report that data as “raw” Likert scores. Likert questions and conversion of specialists’ responses to Anatomic Model Utility Points (AMUPs). Responses of “strongly disagree”, “disagree”, and “neutral” were assigned 0 AMUP points. Responses to preprocedural confidence are assigned negative points, to effectively subtract the impact of the anatomic model post- versus pre-procedure. The maximum AMUP for each patient was 500.

	
17.2 Describe the steps that will be taken to secure the data.
 
All data will be stored on REDCap. During data collection, the research coordinator will record the data directly into REDCap. REDCap which is a server software maintained by Cincinnati Children's Hospital Medical Center (CCHMC) informational technology team. REDCap must be installed on a local web server by CCHMC’s internal IT staff. CCHMC’s server environment is physical/on-premises. CCHMC’s internal IT staff must handle all aspects of REDCap installation, maintenance, and support. The REDCap license is required to install the software. Note, it must be pointed out that much of the security surrounding REDCap has nothing to do with the REDCap software itself but rather is dependent upon the IT infrastructure and environment in which REDCap has been installed. This includes the webserver and database server, the communication between those two servers, and the communication of the web server with the REDCap end-user. REDCap is easily configurable for use and requires minimal infrastructure and setup.
 
REDCap can run on several different operating systems (Linux, Unix, Windows, Mac). To ensure that REDCap users have access only to data and information that they are supposed to have access to within the application, user privileges are utilized within the software. REDCap implements authentication to validate the identity of end-users that log in to the system. CCHMC’s utilizes Shibboleth authentication to provide a single sign-on, external method of authentication. User’s username and password are controlled in CCHMC’s OIM. Users in REDCap are redirected to another webpage to log in, and then are redirected back to REDCap if they authenticated successfully.
 
REDCap contains an auto-logout setting, which is customizable (default auto-logout time is 30 minutes) and will automatically log a user out of the system if they have not had any activity (e.g., clicking, typing, moving the mouse) on their current web page for the set amount of time. This prevents someone else from accessing their account and their project data if they leave a workstation without properly logging out or closing their browser window. CCHMC’s REDCap will store all data captured in REDCap on its own servers. Therefore, all project data is stored and hosted at CCHMC, and no project data is ever transmitted at any time by REDCap from CCHMC to another institution or organization. REDCap does not employ any kind of

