	
6.1 Thoroughly describe the study design.
 
We plan to conduct a randomized controlled trial on trauma patients brought to either UCMC or UC HH OMS for treatment of isolated mandibular fractures. This study plans to elucidate whether the utilization of 3D models during operations where effective in minimizing both OR time and operational costs. Subjects will be identified based off the initial physical assessments made by surgical specialists from OMS, Plastic Surgery, and otolaryngology. Once the subjects are identified the research coordinator will conduct a screening of the patient to ensure they meet the inclusion/ exclusion criteria for the study and then randomize the patient into either normal standard of care for surgical repair of the fractured mandible or normal standard of care for surgical repair of the fractured mandible aided by a 3D printed model of the patient's jaw. Any chart reviewing will be conducted from existing electronic medical records maintained by UC Health EPIC and OMS Vision. All the following data would be based on the patient's condition at the time of surgery.

	
Following completion of the procedure, for the surgeons who received aide via the 3D model they will be asked to answer a brief Likert Scale survey outlining their thoughts how effectively or ineffectively the model assisted them. In addition to this information, if they feel the model increased efficiency saving time, they will be asked to state how much time they felt was saved. This time differential will be compared to current CPT codes for OR time to understand how much in operational costs were saved by utilizing the models.

6.0 PROCEDURES INVOLVED	

6.2 Detail the procedures being performed, specifically the interaction or intervention with human subjects and/or their identifiable information. Please be clear and concise and provide information relevant to the current study. For
	

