**TEMPLATE: RESEARCH PROTOCOL**

NUMBER	ACTIVE DATE	PAGE
HRP-503	02-04-2020	18 of 35

	
of REDCap allows for close monitoring of data from the study supervisors. Additionally, only the research coordinator will have capability to add or remove data. REDCap allows the coordinator to designate or prevent specific rights to be assigned from team members.
 
17.4 Describe how data or specimens will be handled study wide as outlined below.
 
17.5 What information will be included in the data or associated with the specimens?
 
No specimens will be collected. The information collected will be as follows:
 
 
Procedural Time
 
Cost differential via model utilization
 
3D Printing Likert scale Questions answered by specialist post operatively
 

--	---

	
17.6 Who will have access to the data or specimens?
 
No specimens will be collected. Data access will be restricted to the research coordinator, the principal investigator, and co-investigators
 
17.7 Where and how data or specimens will be stored?
 
No specimens will be collected. As discussed earlier, all the data will be stored on REDCap.
 
17.8 How long the data or specimens will be stored?
 
No specimens will be collected. The data will be stored for the duration of the study, which is expected to take approximately two years, and for the duration of data analysis and peer-reviewed publication, which is expected to take another year. Realistically, the data will be stored for three years.
 
17.9 If applicable, how data or specimens will be transported?
 
Not Applicable.
 
17.10 Who is responsible for receipt or transmission of the data or specimens?
 
Not Applicable.

--	--

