### For surgeons:

The research coordinator will establish a private meeting with each surgical team member involved in the study who will be performing the surgical repair for a mandible fracture. The research coordinator will bring the necessary consent forms for the surgeon's review.

During this appointment the study coordinator will introduce the Likert scale questions that the surgeon will be responsible for answering post- operatively if they are selected to use the 3D model for that procedure. That way if the surgeon elects to remove themselves from the study, they may do so at that present time. If the surgeon agrees to the Likert scale questions, the study coordinator will begin the consenting process.

During the consenting process the research team member will go over all the details and timelines for the study. Contact information will also be provided so if any questions or concerns arise, they can contact the study team.

The study team will ensure that the surgeon is by no way obligated to participate in this study. The procedure and normal post operative standards of care will be provided if the

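### The AMUP score for Outcome 3 subtracts preprocedural confidence, but every stated time for the surgeon's Likert questions is after the operation, so the subtracted value is a retrospective rating

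*Protocol*

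**What the plan says.** Section 5.1 of the protocol lists a subjective Likert rating by the surgeon as Outcome 3. Section 17.1 converts the answers to AMUP, with a stated maximum of 500 per patient, and gives two scoring rules. The first sets a floor: "Responses of “strongly disagree”, “disagree”, and “neutral” were assigned 0 AMUP points". The second builds in a baseline: "Responses to preprocedural confidence are assigned negative points, to effectively subtract the impact of the anatomic model post- versus pre-procedure". Neither the number of items nor the points for an agreement response is given.

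The timing is set elsewhere. Section 6.1: "Following completion of the procedure, for the surgeons who received aide via the 3D model they will be asked to answer" the survey. Section 10.1 says that surgeons from the collaborating divisions "will be consented and recruited to participate in this study by providing their feedback post operatively". Section 17.5, the list of information to be collected, has "3D Printing Likert scale Questions answered by specialist post operatively" and no rating from before the operation. Section 18.1 also puts the consented surgeon's assessment after the procedure is complete. In section 23.3 the coordinator will, at the consent meeting, "introduce the Likert scale questions that the surgeon will be responsible for answering post- operatively". The questions are shown at that meeting, not answered.

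**The concern.** A score that takes prior confidence away from later ratings needs prior confidence to be measured beforehand. If it is asked afterwards, the surgeon rates it knowing how the case went, having handled the model, and on the same occasion as being asked whether the model helped and how much time it saved. The two sides of the difference then share one occasion and one frame of mind, and the lower side is a memory.

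This matters more than usual here because sections 6.1 and 23.3 direct the questions only to surgeons who used the model. No control-arm score exists against which a recall effect could cancel, so the subtraction is the only comparator the AMUP has. Nor can a later analysis plan repair it, since no analysis recovers a baseline that was not recorded in time.

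**Working it through.** The protocol states no figure that can be reproduced here. The check sets the scoring rule against the collection schedule, then follows a shift in recall through the score.

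**Step 1: what the score requires.** Section 17.1 needs at least one confidence rating that refers to the time before the procedure.

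**Step 2: when ratings are taken.** Sections that give a time:
- 6.1 (study design): after the procedure, model arm only.
- 10.1 (screening): feedback after the operation. This is feedback in general and does not name the confidence item.
- 17.5 (data list): after the operation, with nothing listed from before it.
- 18.1 (monitoring): after the procedure is complete.
- 23.3 (surgeon consent): after the operation, if the model is used.

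Sections that mention the questionnaire without giving a time:
- 6.5: "The surgeon assigned to the case will fill out the questionnaire outlining the how effective using the 3D model was during the procedure". The past tense fits completion after surgery but does not state it.
- 14.2: mentions the Likert questions only in connection with surgeons who leave the study.

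No section describes a rating before the operation. Taken together, these passages leave only one occasion on which the preprocedural item can be answered, and by then the surgeon has used the model and finished the case.

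**Step 3: what a recall shift does to the score.** Assume the usual five response levels (the protocol names the lower three) and that the zero floor applies to the confidence item as well. Let agree be worth *a* points and strongly agree *b* points, with 0 < *a* ≤ *b*. Neither value is in the protocol. If s(r) is the points for response r, prior confidence contributes −s(r). Recording r′ from memory in place of the contemporaneous r therefore changes the AMUP by s(r) − s(r′). For one step downward:
- disagree recalled as strongly disagree: 0 − 0 = 0
- neutral recalled as disagree: 0 − 0 = 0
- agree recalled as neutral: *a* − 0 = +*a*
- strongly agree recalled as agree: *b* − *a*, which is zero or positive

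One step upward across the same boundaries gives 0, 0, −*a* and −(*b* − *a*). A shift matters only when it starts from or reaches an agreement response. Remembering less confidence can only raise the AMUP or leave it alone, and remembering more can only lower it or leave it alone. The absolute effect runs from 0 upward, and without *a* and *b* it cannot be turned into points or a share of 500.

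**The case against.** The strongest reply is that recall is an inference. No section says that the confidence item is remembered. The wording of 17.1 could reflect an intended pre-operative rating that the other sections forgot to mention, and the questionnaire itself is not in the document. That is fair as to intent, and a separate pre-operative form cannot be excluded. It does not rescue the text: the data list in 17.5 would then be incomplete and the timing sections would still need correcting.

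A second reply is that the consequence is limited. The hypothesis in section 1.2 concerns operating-room time and time for the critical part of the procedure, neither of which uses AMUP. Section 17.1 also reports raw Likert scores and names no test of AMUP. This stands, and it confines the point to Outcome 3.

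A reader might also infer more than the protocol supports:
- **That the bias favours the model.** It is plausible that prior confidence is remembered as lower after a good case, but nothing in the document establishes a direction, and a difficult case could work the other way.
- **That the bias can be sized.** Supposing 25 to 100 points per response step would give 25/500 = 5% to 100/500 = 20% of the maximum. Those step values have no source in the protocol, and steps between neutral and the responses below it add nothing.
- **That every mention of the questionnaire places it after surgery.** Sections 6.5 and 14.2 give no time.

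**Conclusion.** The point holds as a conflict between the scoring rule in 17.1 and the collection schedule in 6.1, 10.1, 17.5, 18.1 and 23.3. Carried out as written, the subtracted component is a retrospective rating, and the AMUP difference is open to recall bias in either direction. The size is zero or more per case and cannot be computed from the protocol. The conclusion rests on two premises: that no pre-operative form exists beyond what the protocol describes, and that the zero floor covers the confidence item. The second bears only on how often a shift changes the score, not on whether the baseline is sound.

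The result known to the surgeon is the operative course, not the six-week examination. Total and critical-part operating-room time and the clinical outcome are untouched. The change should be made for the sake of Outcome 3, but the point does not threaten the tested hypothesis.

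**What to change.** Split the questionnaire by time:
- The surgeon rates the preprocedural-confidence item or items after reviewing the CT and before being shown the 3D model. Section 18.7 already says that the imaging has been reviewed by then, so the moment exists.
- The research coordinator records that rating in REDCap at that time. Sections 17.2 and 17.3 have the coordinator record the data and reserve adding or removing it to that role.
- The remaining items are completed after the procedure.
- The AMUP subtraction uses only the rating recorded beforehand.
- Sections 6.1, 10.1, 17.5, 18.1 and 23.3 are aligned with this. Changing only some of them would leave the conflict in place.

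If the sponsor prefers a single post-operative questionnaire, 17.1 should call the item a retrospective rating and drop the statement that it subtracts the model's impact.

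The cost is one short, earlier rating per model-arm case (50 planned) plus protocol wording. Where the early rating is missing, only raw Likert scores would be reported. Even a true pre-rating would not fully isolate the model's effect: with no control-arm ratings, the change also includes whatever completing the operation does to confidence. The write-up should say so.
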